#### **9.4.2.2 Key Secondary Endpoints**

##### **9.4.2.2.1 PAINS-pNF chronic target PN pain intensity**

The key secondary estimand is the difference of the means in the change from baseline in PAINS-pNF chronic target PN pain intensity score at Cycle 12 between selumetinib and placebo, amongst participants with a PAINS-pNF chronic target PN pain intensity score  $\geq 3$  at

baseline (Pain FAS) and at least one post-baseline average cycle PAINS-pNF chronic target PN pain intensity score. Intercurrent events are addressed as follows:

- Changes to participants' chronic PN pain medication will be included assuming the treatment policy strategy to the intercurrent event of changes in participant's chronic PN pain medication.
- Post randomised study intervention discontinuation PAINS-pNF scores will not be collected and will be modelled through direct likelihood techniques assuming a hypothetical strategy to the intercurrent event of randomised study intervention discontinuation prior to end of cycle 12 due to any reason.
- PAINS-pNF scores after early crossover from placebo to selumetinib in participants with documented progression on imaging (as determined by ICR per REiNS criteria) will be set to missing assuming a while-on-treatment strategy to the intercurrent event of early crossover from placebo to selumetinib.
- PAINS-pNF scores after the first 28 days of a prolonged study intervention interruption until day prior to study intervention recommencement will be set to missing assuming a while-on-treatment strategy to the intercurrent event of prolonged study intervention interruption.
- PAINS-pNF scores after a target PN resection will be included in the analysis assuming a treatment policy approach to the intercurrent event of target PN resection.

A PAINS-pNF chronic target PN pain intensity score  $\geq 3$  at baseline is used to take into account ceiling effects. Participants with a PAINS-pNF chronic target PN pain intensity score  $< 3$  at baseline have very little or no possibility of improvement.

The response variable for a cycle will be the average cycle PAINS-pNF chronic target PN pain score change from baseline defined as the average of the available daily PAINS-pNF chronic target PN pain scores for the 28 days up to and including the last day of the cycle minus the baseline PAINS-pNF chronic target PN pain score. The average cycle PAINS-pNF chronic target PN pain score will only be derived if the participant meets the criteria of having at least 4 daily pain scores out of 7 days for at least 3 non-overlapping 7-day periods in the 28-day cycle. Baseline PAINS-pNF chronic target PN pain score is defined as the average of the available daily PAINS-pNF chronic target PN pain scores in the screening period. During this time, participants must complete their pain diary for at least 4 days out of 7 days for at least 2 non-overlapping 7-day periods in order to determine the participant's average baseline chronic target PN pain intensity score.

## Scoring

Each of the two items on the PAINS-pNF (usual [chronic] pain and spikes of PN pain) are treated as an individual score ranging from 0 to 10. For example, when administered daily for 7 days consecutively, this results in 7 usual (chronic) PN pain scores and 7 spikes of PN pain scores.

## Analysis Methods

For each participant, mean change from baseline in PAINS-pNF chronic target PN pain intensity score at each cycle will be calculated using the average cycle PAINS-pNF chronic target PN pain score minus baseline PAINS-pNF chronic target PN pain score.

The difference in the mean change from baseline at Cycle 12 will be analysed for PAINS-pNF chronic target PN pain intensity using a mixed model repeated measures (MMRM) analysis. The MMRM model will include treatment, cycle number and geographical region as categorical fixed effects, the baseline PAINS-pNF chronic target PN pain intensity score as a continuous covariate and treatment-by-cycle number and baseline PAINS-pNF score-by-cycle number interactions. Parameters will be estimated with the restricted maximum likelihood (REML) approach and the Kenward-Roger approximation is used to estimate the degrees of freedom. An unstructured covariance matrix will be used to allow for unequal treatment variance and to model the correlation between different treatment measurements within the same subject. If the fit of the unstructured covariance structure fails to converge, the following covariance structures will be used in order until convergence is reached: toeplitz with heterogeneity, autoregressive with heterogeneity, toeplitz, autoregressive and compound symmetry.

The approach to examine missingness will be described in the SAP.

In addition, supplementary analyses for alternative estimands will be detailed in the SAP, including specifying a composite strategy for the intercurrent events of study intervention discontinuation and increase in chronic PN pain medication (based on data collected in the e-Diary and investigator's assessment of pain medication as outlined in Section 8.1.8.3) such that data not collected post study intervention discontinuation and potential confounding from pain medication are addressed.

### 9.4.2.2.2 PlexiQoL

The key secondary estimand is the difference of the means in the change from baseline in PlexiQOL total score at Cycle 12 between selumetinib and placebo, amongst FAS participants with an baseline PlexiQOL total score and at least one post-baseline PlexiQOL total score. Intercurrent events are addressed as follows:

- Post randomised study intervention discontinuation PlexiQOL scores will not be collected and will be modelled through direct likelihood techniques assuming a hypothetical strategy to the intercurrent event of randomised study intervention discontinuation prior to end of cycle 12 due to any reason.
- PlexiQOL scores after early crossover from placebo to selumetinib in participants with documented progression on imaging (as determined by ICR per REiNS criteria) will be set to missing assuming a while-on-treatment strategy to the intercurrent event of early crossover from placebo to selumetinib.
- PlexiQOL scores after the first 28 days of a prolonged study intervention interruption until day prior to study intervention recommencement will be set to missing assuming a while-on-treatment strategy to the intercurrent event of prolonged study intervention interruption.
- PlexiQOL scores after a target PN resection will be included in the analysis assuming a treatment policy approach to the intercurrent event of target PN resection.

The response variable for a specific cycle will be the PlexiQOL change from baseline defined as the PlexiQOL total score at that cycle minus the baseline PlexiQOL total score.

### **Scoring**

Each statement on the PlexiQoL is given a score of 1 = True or 0 = Not true. A score of “1” is given where the item is affirmed, indicating adverse quality of life. According to the PlexiQoL user manual, it is recommended that for respondents with between one and three missing responses (that is, cases with no more than 20% missing data), the total score is calculated as follows: all item scores are summed to give a total score that ranges from 0 (good QoL) to 18 (poor QoL). This total score is then divided by the number of non-missing items and multiplied by 18. Cases with more than three missing responses cannot be allocated a total score.

Difference in change from baseline in PlexiQoL items between selumetinib and placebo will be evaluated at post-baseline cycles and overall over the randomised treatment period.

The change from baseline in PlexiQoL total score over the duration of the study will also be evaluated.

### **Analysis Methods**

For each participant, change from baseline in PlexiQOL total score at the end of each cycle where PlexiQOL is measured during the randomised period (cycles 2, 4, 8 and 12) will be calculated.

The difference in the mean change from baseline at Cycle 12 will be analysed for PlexiQOL total score using a MMRM analysis. The MMRM model will include treatment, cycle number and geographical region as categorical fixed effects, the baseline PlexiQOL total score as a continuous covariate and treatment-by-cycle number and baseline PlexiQOL total score-by-cycle number interactions. Parameters will be estimated with the restricted maximum likelihood (REML) approach and the Kenward-Roger approximation is used to estimate the degrees of freedom. An unstructured covariance matrix will be used to allow for unequal treatment variance and to model the correlation between different treatment measurements within the same subject. If the fit of the unstructured covariance structure fails to converge, the following covariance structures will be used in order until convergence is reached: toeplitz with heterogeneity, autoregressive with heterogeneity, toeplitz, autoregressive and compound symmetry.

The approach to examine missingness will be described in the SAP.

In addition, supplementary analyses for alternative estimands will be detailed in the SAP,

Full details of the analysis of PlexiQoL items will be documented in the SAP.

#### **9.4.2.3 Secondary Endpoints**

##### **9.4.2.3.1 Objective Response Rate (single-arm)**

Objective response rate is defined as described in Section [9.4.2.1.2](#).

This ORR analysis will include all participants randomised to selumetinib with measurable target PN at baseline per ICR and who received at least one dose of selumetinib (Selumetinib FAS), ie, single arm assessment of ORR. Data obtained while on-treatment from first selumetinib dose up until progression, or the last evaluable assessment in the absence of progression, will be included in the assessment of ORR. Any confirmed CR or a confirmed PR which occurred after a subsequent NF1-PN treatment (following study intervention discontinuation) will not be included in the numerator for the ORR calculation (where the selumetinib FAS will be the denominator).

Supportive evidence of the ORR (single-arm) will include:

- A supplementary analysis including all participants with measurable target PN at baseline per ICR who received at least one dose of selumetinib (Extended selumetinib FAS). In this analysis, the baseline MRI scan for participants randomised to placebo will be defined as the last MRI scan performed on placebo treatment prior to crossing over to selumetinib treatment.

- The BOR, defined as the best objective response recorded from the start of study intervention until progression or the last evaluable MRI assessment in the absence of progression, will also be summarised by category (confirmed CR, CR, confirmed PR, PR, stable disease, PD, or NE) and treatment arm.

## **Analysis Methods**

ORR will be presented with corresponding two-sided exact 95% CI based on the Clopper Pearson methods ([Clopper and Pearson 1934](#)).

The BOR will be summarised with descriptive statistics for both the selumetinib FAS and the extended selumetinib FAS.

Full details of the analyses and supportive analyses will be documented in the SAP.

### **9.4.2.3.2 Duration of Response**

Duration of Response is derived using while on-treatment MRI volumetric assessments. The DoR will be defined as the time from the date of first documented response (which is subsequently confirmed) until date of documented progression as assessed by ICR per REiNS criteria or death due to any cause (ie, date of PFS event or censoring – date of first documented response + 1).

The analysis will include all participants randomised to selumetinib with measurable target PN at baseline per ICR who received at least one dose of selumetinib (Selumetinib FAS) and with a confirmed CR or confirmed PR prior to study intervention discontinuation. Full details of the derivation of DoR while on-treatment, and censoring rules will be documented in the SAP.

A supplementary analysis will be performed including all participants who received at least one dose of selumetinib and with a confirmed CR or confirmed PR prior to study intervention discontinuation. In this analysis, the baseline MRI scan for participants randomised to placebo will be defined as the last MRI scan performed on placebo treatment prior to crossing over to selumetinib treatment.

## **Analysis Methods**

Descriptive data will be provided for the DoR in responding participants, including the associated Kaplan-Meier curves. Full details of the DoR summaries will be documented in the SAP.

### **9.4.2.3.3 Progression Free Survival**

Progression free survival will be derived using while on-treatment MRI volumetric assessments and is defined as the time from the date of first selumetinib dose until date of

progression by ICR per REiNS criteria or death (due to any cause), ie, date of event or censoring – date of the first dose of selumetinib + 1.

Participants who have not progressed or died at the time of analysis will be censored at the time of the latest date of assessment from their last evaluable REiNS assessment.

The analysis will include all participants randomised to selumetinib with measurable target PN at baseline per ICR who received at least one dose of selumetinib (Selumetinib FAS).

A supplementary analysis will be performed including all participants with measurable target PN at baseline per ICR who received at least one dose of selumetinib (Extended Selumetinib FAS). In this analysis, the baseline MRI scan for participants randomised to placebo will be defined as the last MRI scan performed on placebo treatment prior to crossing over to selumetinib treatment.

Full detail for the derivation of PFS while on-treatment and censoring rules will be documented in the SAP.

### **Analysis Methods**

Descriptive data will be provided for PFS, including the associated Kaplan-Meier curve. Full details of PFS summaries will be documented in the SAP.

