### **Analysis Methods**

Descriptive data will be provided for the TTP, including the associated Kaplan-Meier curves.

Full details of TTP summaries will be documented in the SAP.

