4.2.4.4 Primary Analysis of DOR

Kaplan-Meier (KM) plots of DOR will be presented including a patients-at-risk table. Median DOR, 25th and 75th percentiles, and 95% CI will also be calculated together with the estimated percentage remaining in response and 95% CI using the KM method and presented in a summary table. The number and percentage of responding patients remaining in response at 8, 12, 16, 20, and 24 months post-response and every 6 months thereafter will also be summarised.

Only patients randomised to selumetinib (Selumetinib FAS) with a cCR or cPR prior to selumetinib discontinuation will be included in this analysis. Data are included as outlined in Sections 4.2.4.1 and 4.2.4.2, adhering to the intercurrent event strategy (refer to Section 4.2.4.3).

Swimmer plots that clearly show the profile of each patient who responds will also be produced. Additional graphical symbols to depict the start of the objective response, PD or death, and subsequent therapy will be added. “On treatment” will be designated with different colour from “post-treatment.”

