4.2.5.4 Primary Analysis of PFS

A KM plot of PFS will be presented including a patients-at-risk table. The percentage of PFS at Months 4, 8, 12, 16, 20, and 24 and every 6 months thereafter will be summarised based on the KM method. If more than 50% of patients progress in either arm, the median PFS and 95% CIs will also be calculated using the KM method and presented in the summary table.

Data are summarised and analysed using the Selumetinib FAS. Data are included as outlined in Sections 4.2.5.1 and 4.2.5.2, adhering to the intercurrent event strategy (refer to Section 4.2.5.3).

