4.2.6.4 Primary Analysis of TTP

A KM plot of TTP will be presented including a patients-at-risk table. The percentage TTP at Months 4, 8, 12, 16, 20, and 24 and every 6 months thereafter will be summarised based on the KM method. If more than 50% of patients progress in either arm, the median TTP and 95% CIs will also be calculated using the KM method and presented in the summary table.

Data are summarised and analysed using the Selumetinib FAS. Data are included as outlined in Sections [4.2.6.1](#) and [4.2.6.2](#), adhering to the intercurrent event strategy (refer to Section [4.2.6.3](#)).

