4.2.7.4 Primary Analysis of Time to Response

A KM plot of TTR will be presented including a Patients-at-Risk table. The percentage TTR at months 4, 8, 12, 16, 20 and 24, and every 6 months thereafter will be summarised based on the KM method. Median TTR and 95% CIs will also be calculated using the KM method and presented in the summary table.

Data is summarised and analysed using the Selumetinib FAS. Data is included as outlined in Section 4.2.7.1 adhering to the intercurrent event strategy (refer to Section 4.2.7.3).

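### SAP 4.2.5.4 and 4.2.6.4 tie median PFS and TTP to a crude count of progressions above 50%, which can only withhold a Kaplan-Meier median that has been reached

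*Protocol*

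**What the plan says.** Protocol 9.4.2.3.3 says "Descriptive data will be provided for PFS, including the associated Kaplan-Meier curve" and 9.4.2.3.4 says "Descriptive data will be provided for the TTP, including the associated Kaplan-Meier curves". Both leave full details to the SAP, so the rule is in the SAP and not in the protocol.

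- SAP 4.2.5.4 (PFS): "If more than 50% of patients progress in either arm, the median PFS and 95% CIs will also be calculated using the KM method".
- SAP 4.2.6.4 (TTP): "If more than 50% of patients progress in either arm, the median TTP and 95% CIs will also be calculated using the KM method".
- SAP 4.2.16.3 (PFS during the randomised period, two arms) repeats the condition.

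Whatever the event count, 4.2.5.4 and 4.2.6.4 also give a KM plot with an at-risk table, and KM percentages at Months 4, 8, 12, 16, 20 and 24 and every six months thereafter. No confidence interval is specified for those percentages.

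The DOR section (4.2.4.4) sets no such condition: "Median DOR, 25th and 75th percentiles, and 95% CI will also be calculated". The endpoint table in SAP 4.2 names the percentage at specified timepoints as the population-level summary for PFS and TTP, and the median for DOR.

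**The concern.** A KM median exists as soon as the KM estimate falls to 50%. With censoring, that can happen before half of all patients have an observed event. Here censoring is built in. Patients without an event are censored at their last evaluable MRI, and an event after two or more missed assessments is censored too (SAP 4.2.5.2). Scans after study drug is stopped are not used (SAP 3.3.2.1), and the data cut-off truncates follow-up.

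A threshold on the raw share of patients who progress is therefore a different test from whether the median can be estimated. Two wording faults add to this. PFS counts death as an event (SAP 4.2.5.1), but the condition counts progressions only. And the Selumetinib FAS has one arm, so the reference to either arm has no meaning in 4.2.5.4 and 4.2.6.4.

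At stake is whether the summary tables for two secondary objectives carry a median and its interval. As written, that depends partly on how much censoring occurred.

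**Working it through.** The documents state no PFS or TTP event count, rate or median, so there is no figure of the plan's own to reproduce.

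**Threshold.** The Selumetinib FAS is planned at 73 patients. Half of 73 is 36.5, so the rule needs at least 37 progressions.

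**Direction of the error.** Let *d* of *n* patients have events. At each event the KM curve drops by S/r, with S the estimate just before and r the number at risk. Censoring removes patients from r without lowering S, so each drop is at least 1/n. After the last event, S ≤ 1 − d/n. If d/n exceeds 0.5, S is below 0.5 and the median is reached. The converse fails. Counting the progressions that enter the analysis as events, the rule can therefore err only by withholding.

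**Hand example.** Ten patients, with one event and one censoring at each of months 4, 8, 12, 16 and 20:

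- Month 4: 9/10 = 0.900
- Month 8: 0.900 × 7/8 = 0.788
- Month 12: 0.788 × 5/6 = 0.656
- Month 16: 0.656 × 3/4 = 0.492

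The median is reached at month 16 after four events. Only 5 of 10 patients ever progress, which is not more than 50%, so the rule withholds it.

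**Simulation of the final data cut-off.** From the documents: 73 patients; scans every 4 cycles to Cycle 24, then every 6; follow-up of at least 24 cycles (24 × 28 / 30.4375 = 22.1 months); censoring at the last scan before discontinuation or data cut-off. Assumed, because the documents do not say: exponential progression times, dated at the next scheduled scan; uniform accrual over 12 or 24 months; 10%, 20% or 35% discontinuing by Cycle 12 without regard to progression; no deaths. There were 1,000 trials per scenario. Ranges run over the six accrual and discontinuation combinations.

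| Assumed true median (months) | Median reached but withheld, all trials | Withheld, among trials that reached it |
|---|---|---|
| 12 | 0–47% | 0–47% |
| 18 | 4–92% | 4–97% |
| 24 | 43–91% | 44–100% |
| 30 | 42–81% | 84–100% |
| 36 | 26–67% | 96–100% |
| 48 | 11–31% | 100% |
| 72 | 5–10% | 100% |
| 120 | 1–4% | 100% |

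No trial had more than 50% crude events and an unreached KM median, as the inequality requires.

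**Effect of reporting whenever reached.** With 20% discontinuation and 12-month accrual, the chance that the table shows a median would change from 97% to 100% at a true median of 12 months, from 42% to 99% at 18, from 5% to 81% at 24, from 0% to 26% at 36, and from 0% to 5% at 72.

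**The case against.** The best defence is that little is lost. The median is an addition to the declared summary, which is the percentage at timepoints. The curve, at-risk table and landmark percentages are always produced, and individual PFS and TTP times are listed at later cut-offs (SAP 4.2.5.5, 4.2.6.5). Neither endpoint is in the testing hierarchy of SAP 3.3.7. All of this stands and limits the severity. It does not remove the point: if the condition fails, 4.2.5.4 and 4.2.6.4 specify no confidence interval at all, and a median read off a plot does not supply one.

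Progression may also be slow. Randomised-period PFS is analysed only if at least 5 events occur across both groups (SAP 4.2.16.1). Cycle 12 ends at 12 × 28 / 30.4375 = 11.0 months. Under an exponential model, expected progressions by then among 73 patients are 73 × (1 − 2^(−11.0/m)): about 20 for m = 24 months, 14 for m = 36 and 4.5 for m = 120. A gate of 5 sits more easily with slow progression, where the rule seldom matters. It is a floor and not a forecast, but it does count against assuming a median of 18 to 36 months.

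A median reached with at most half the patients having events can rest on few at risk. Censoring at discontinuation may also be informative, since the investigator may stop drug for progression by their own judgement (Protocol 7.1) while the event is defined by central review. Both cautions are fair. They apply equally to the curve, which is shown anyway, and a crude count does not screen for either.

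The TTR median is also unconditional ("Median TTR and 95% CIs will also be calculated using the KM method and presented in the summary table"), which might look like a second inconsistency. It is a poor comparator: only confirmed responders enter TTR, so every patient has the event.

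**Conclusion.** The point holds as a low-severity correction to the SAP. The condition in 4.2.5.4 and 4.2.6.4 is the wrong test for whether a median can be reported, and its error runs one way. That follows from algebra and needs no assumption about rates. Its frequency does need assumptions: about 0% to 92% over true medians of 12 to 120 months, largest near 18 to 36 months, under exponential progression, independent discontinuation and no deaths.

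A reader might infer that medians will often be withheld, or that headline results of the trial are at risk. The documents support neither. They give no PFS or TTP rate, and the SAP declares the percentages at timepoints as the summary. The loss is confined to the tabulated median and its interval.

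In 4.2.16.3 the effect is probably smaller. That analysis spans about 11 months, and most censoring should fall at the end of the period. It was not computed. The reference to either arm is correct there.

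**What to change.** In SAP 4.2.5.4, 4.2.6.4 and 4.2.16.3, replace the condition with wording such as: the median and its 95% CI will be taken from the KM estimate; where that estimate does not fall to 50%, the median will be given as not reached, with the lower confidence limit if estimable. This matches the unconditional DOR median in 4.2.4.4 and, for PFS, removes the question of whether deaths count. Delete *in either arm* from 4.2.5.4 and 4.2.6.4 only.

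The cost is SAP wording; the KM analysis is already planned. The small downside is that a median reached late may rest on few patients, so it should be read with the at-risk table that 4.2.5.4 and 4.2.6.4 already require.
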